1. Obtain IRB approval 2. Distribute fliers around the HSC building and send an email through the wellness office to all faculty and staff in the HSC building. 3. Make an Excel file of all interested participants. 4. Contact participants to ensure eligibility. 5. Randomly assign participants to one

of three groups: (1) Sit-Stand station with 4-6 educational sessions and instructions to alternate standing and sitting every 90 minutes, (2) Sit-stand station with 4-6 educational sessions and instructions to stand for 20-30 minutes every hour, (3) Sit-stand station with 4-6 educational sessions with instructions to alternate sitting and standing every hour. *all groups will attend same educational sessions. 5. Schedule meeting to review and collect informed consent documents and distribute and collect the Stages of Change Questionnaire, the Cornell Musculoskeletal Discomfort Questionnaire, and the Movement at Work Questionnaire. 6.Install sit-stand work stations in each participants office space. 7. Provide educational sessions on use of sit-stand workstations and the behavioral monitoring self-report form. 8. Within 2 weeks of installation of sit-stand workstation complete observation with each participant to ensure safe and efficient use. 9. Collect behavioral

monitoring self-report forms weekly from all participants. 10. Send reminder email or text prompts to participants for designated time intervals for the group which they are enrolled. 11. After 3 months re-distribute the Stages of Change Questionnaire, Cornell, and Movement at Work Questionnaires. 12. After 6 months re-distribute the Stages of Change Questionnaire, Cornell, and Movement at Work Questionnaire, and Movement at Work Questionnaire, Cornell, and Movement at Work Questionnaire, Cornell, and Movement at Work Questionnaires and collect all sit-stand workstations. 13. Clean and analyze data. 14. Write up report and prepare for presentation or publication.

Please describe the investigational procedures that will be performed throughout the duration of the study.

Observation of participants in natural working environment, questionnaires/surveys.

Please describe the standard of care procedures that will be performed throughout the duration of the study.

All participants will be given the same questionnaires/surveys and behavioral tracking forms. All participants will also receive the same education on the use of the sit-stand workstation and other helpful office ergonomic tips.

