Will you be assigning or randomizing participants to groups or conditions (e.g., control, placebo)?

Yes

Describe the group assignment.

All the groups will receive the same educational sessions and complete the same questionnaires. The only difference in groups is in the instructions for alternating sitstand time. One group will alternate every 20-30minutes, one every 60 minutes, and one every 90 minutes.

Describe what is known about this topic and why this study is needed. Please include at least two reference citations to support your rationale.

Prolonged sedentary activity and a reduction in human energy expenditure are detrimental to many domains of health. In recent years, "populations have become increasingly sedentary, with many adults spending a minimum of 70% of their waking hours sitting" with little neuromuscular stimulation (Owen, Sparling, Healy, Dunstan and Matthews, 2010). Desk-based workers make up a relatively large proportion of this population making them an important target for health promotion initiatives focusing on solutions to implement healthy workspaces and foster a more active business community. Although there is rich literature on the many benefits of reducing sedentary behavior, there is a call for further research on the feasibility and long-term effects of sitstand desks on achieving this reduction in office settings (Grunseit, et al., 2012). Occupational therapy practitioners have the capacity to address this health issue with their background in community disease prevention and health promotion to improve an individual's wellness and quality of life. More research is also needed to establish the specific role of occupational therapy in workplace wellness interventions and apply

occupation in its natural settings such as the workplace by maximizing performance, function, and wellness. By implementing sit-stand work stations with educational sessions into offices of desk-based employees long-term, we will better be able to analyze how effective this strategy is at decreasing sitting time and measure health and behavioral outcomes associated with using this intervention. Grunseit, A. C., Chau, J. Y.-Y., van der Ploeg,

H. P., & Bauman, A. (2013). "Thinking on your feet": A qualitative evaluation of sit-stand desks in an Australian workplace. BMC Public Health, 13, 365. Owen, N., Sparling, P. B., Healy, G. N.,

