Dunstan, D. W., & Matthews, C. E. (2010). Sedentary Behavior: Emerging Evidence for a New Health Risk. Mayo Clinic Proceedings, 85(12), 1138-1141. doi:10.4065/mcp.2010.0444

What method are you going to use to analyze the data?

Data will be coded and analyzed using a statistical software program. Any qualitative data that is collected will be member checked.

Expedited Review

Is this study only minimal risk?

Yes

Does the research qualify for Expedited Review Category 1 - use of FDA-approved medical device?

Does the research qualify for Expedited Review Category 2 - blood sample collection?

No

Does the research qualify for Expedited Review Category 3 - noninvasive collection of biological specimens?

Does the research qualify for Expedited Review Category 4 - noninvasive standard care procedures?

No

Does the research qualify for Expedited Review Category 5 - evaluation of data (e.g., medical records review)?" No Does the research qualify for Expedited Review Category 6 - voice, video, digital, or image recordings?

Does the research qualify for Expedited Review Category 7 - behavior, surveys, interviews, etc.?

Briefly describe how the research meets the requirements of the expedited category(ies) selected.

Participants will be required to complete multiple questionnaires as they participate in the intervention. The questionnaires will be assessing changes in behavior, movement at work, and discomfort at work.

Will subjects intentionally be deceived as to the purpose of the study?

No

Does the study involve intervention and/or manipulation of the subjects or the subjects' environment (e.g., educational intervention or training, experimental or quasi-experimental design)? Yes

Describe how and where researchers will interact with participants, explaining how these interactions will be kept private.

Researchers will interact with participants on an individual basis in the participants private office space. In the event that the participant does not have a private office a private space will be reserved at the participants request.

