Describe and assess any potential possibilities for risk or harm to the subjects as a result of their participation in the research, including discomforts, hazards, or inconveniences to the subjects. The primary inconvenience for the participants will be the need for them to clear a space to install the sit-stand work station at their desks. Depending on what group the participant is in, they will be asked to track how often they stand throughout the day which could be an inconvenience or potential discomfort. The sit-stand desk does have mechanical parts that could potentially pinch or injure a participant if not used correctly.

Is the research categorized as interventional medical research? No

HIPAA

Does the research involve protected health information (PHI)?

Yes

Will the HIPAA and consent forms be combined? If not, attach a separate HIPAA Authorization to the Notes & Attachments page. Yes

Are you requesting a HIPAA waiver? If yes, attach a HIPAA Waiver Form on the Notes & Attachments page.

No

Will the research being conducted at a covered entity require authorization from the subject? If yes, attach a HIPAA Form on the Notes & Attachments page - only if a combined consent with HIPAA is not used.

Are you transferring identifiable data to or from another institution? If yes, attach a signed and WVU Legal Counsel approved HIPAA Data Use Agreement Form on the Notes & Attachments page.

Will the research being conducted at a covered entity involve data that is de-identified? If yes, attach a HIPAA De-Identification Certification Form on the Notes & Attachments page. You can find the form here (this is only for NHSR studies). No

Will the study include deceased individuals? If yes, attach a HIPAA Decedents Form on the Notes & Attachments page.

Will data/samples with identifiers be received from another entity? If yes, attach a signed, Legal Counsel approved HIPAA Data Use Agreement Form on the Notes & Attachments page.

No

Subjects

Will any of the subjects be less than 18 years old?

No

Indicate the maximum number of subjects to be enrolled or medical records to be reviewed at all sites by the WVU or VAMC research team. 20

Provide a rationale for choosing your sample size.

This study will consist of 3 groups of 6 individuals receiving the sit-stand workstation. The workstations are being donated to us to complete the research. And 18-20 workstations is the max that we can receive.

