State the requirement(s) to become a participant in the study (e.g., age range, sex, language spoken, class enrollment/ranking).

Participants must spend > 50% of their work day seated at the computer. Participants can be male or female and must be ages 18 years or older. Participants must be primarily English speaking. Participants must work within the Health Sciences Center building at West Virginia University.

Explain why selection of participants will be equitable addressing gender, ethnicity, and/or race of subjects.

Attempts will be made to choose 50% males and 50% females for the study. However, given

the nature of the work it is probable that we will have a higher percentage of females than males enrolled. No one will be ineligible based on race or ethnicity.

In outline format and chronological order, describe what will be done to identify and recruit participants (e.g., A, B, C or 1, 2, 3).

1. Fliers will be distributed throughout the HSC building and an email will be sent from the wellness program to all HSC faculty and staff. 2. Interested participants will contact a member of the research team who will verify their eligibility to participate. 3. If eligible, participants will placed on

a list in Excel with an email address or phone number to be contacted. 4. Participants will then be randomly drawn from the list and contacted to participate in the study. The team will draw 9-10 males and 9-10 females to participate. 5. In the event that there are 20 or fewer participants who are eligible all will be contacted to participate regardless of gender.

Will your study target any of the following vulnerable groups: cognitively impaired, pregnant women and fetuses, or prisoners?

No

Does this research involve participants who could be coerced or unduly influenced, such as current students/employees of research team members? No

Does the protocol deal with cancer prevention, treatment, or diagnosis (including surveys)?

No

Has this protocol been reviewed by Clinical Trials Working Group (CTWG)? If yes, please attach the CTWG's correspondence on the Notes & Attachments page. No

Consent Procedures

Will SIGNED informed consent be obtained from subjects (all or in part)?

Yes

Will the informed consent form be translated into any other language(s)?

No

Is a waiver of informed consent being requested (i.e., there will be no consent process at all)?

No

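### Room-sharing is neither recorded nor considered in the draw or the randomisation, so enrolled room-mates could end up on different visible schedules and dilute the only randomised contrast by an unmeasured amount

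*Combined protocol and SAP*

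**What the plan says.** All references are to the combined protocol and SAP.

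- **Setting.** The Expedited Review section, describing where researchers meet participants, takes the participant's private office as the usual place and then adds: "In the event that the participant does not have a private office a private space will be reserved at the participants request". The numbered procedures in the Design section include: "Install sit-stand work stations in each participants office space". The workstations are collected after 6 months.
- **Randomised contrast.** The group assignment answer states: "The only difference in groups is in the instructions for alternating sitstand time".
- **Unit of allocation.** The procedures give it as "Randomly assign participants to one" of three groups. Room, office and department are not mentioned.
- **Selection.** In the recruitment outline (Subjects section), eligible volunteers go on an Excel list with an email address or phone number. Item 4 continues: "Participants will then be randomly drawn from the list and contacted to participate in the study". The draw is organised by sex. Under item 5, if 20 or fewer are eligible, all are contacted.
- **Size.** "This study will consist of 3 groups of 6 individuals receiving the sit-stand workstation". The ceiling is the supply of donated desks: "And 18-20 workstations is the max that we can receive".
- **Features that help keep the groups apart.** Step 10 of the procedures sends reminders timed to the participant's own group. Step 9 collects self-report forms weekly.

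The procedures and the group assignment answer describe one of the three schedules differently, and the two need to be reconciled. The calculation below does not depend on which description is meant.

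**The concern.** A desk that goes up and down is visible to anyone in the room. If two participants share a room and follow different schedules, each receives the other's cue every working day for 6 months. Any drift toward the room-mate's timing moves the group means together and biases the comparison of schedules toward no difference. That comparison is all the trial randomises, so the loss would fall directly on its main question.

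This route is separate from the educational sessions that all groups attend, and changing how those sessions are run would not remove it. As the list stands, the investigators would not know afterwards whether any room-mates had been enrolled.

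**Working it through.** **Inputs from the documents.** Three groups of 6, so 3 × 6 = 18, which reproduces the plan's figure; the maximum is 20. Allocation is by individual. The protocol gives no significance level, power, effect size or standard deviation, so there is no power figure to reproduce.

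**Assumed inputs.** The number *k* of enrolled room-sharing pairs (0 to 3) and the fraction *f* of the way that a person in a mismatched pair moves toward the room-mate's schedule. The documents give neither.

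**Step 1. Chance that two enrolled room-mates differ.** Once the first is placed, 17 places remain, 12 of them in the other two groups: 12/17 = 0.706. With 20 people split 7/7/6 it is 0.700. With simple randomisation it is 2/3 = 0.667.

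**Step 2. Expected share of participants in a mismatched pair.** q = (2k/18) × (12/17). The chance of at least one mismatched pair, confirmed by simulation, is in the table below.

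**Step 3. Shrinkage of the between-group difference.** Let the group means be μA, μB and μC. A mismatched person in group A has a room-mate in B or C with equal probability. If both members of each mismatched pair move a fraction *f*, the expected mean of group A is

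μA(1 − qf) + qf(μB + μC)/2,

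and likewise for B. Subtracting, μC cancels:

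A − B = (μA − μB)(1 − qf − qf/2) = (μA − μB)(1 − 1.5qf).

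The shrinkage is therefore 1.5qf. The factor exceeds 1 because both group means move. If only one member of each pair moves, it is half of this, 0.75qf.

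| Enrolled pairs (assumed) | At least one mismatched pair | q | Both move halfway | One moves halfway |
|---|---|---|---|---|
| 0 | 0% | 0% | 0% | 0% |
| 1 | 71% | 7.8% | 5.9% | 2.9% |
| 2 | 91% | 15.7% | 11.8% | 5.9% |
| 3 | 97% | 23.5% | 17.6% | 8.8% |

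Example for 3 pairs, both moving halfway: 1.5 × 0.235 × 0.5 = 0.176. Simulated random allocations agree with the formula.

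**Step 4. What this does to power.** Assume a two-sided 5% t-test of 6 against 6. A standardised difference of about 1.80 is needed for 80% power. At that difference, with 94%, 88% or 82% of the contrast retained (1, 2 or 3 pairs, both moving halfway), power is about 75%, 70% or 64%. At a standardised difference of 0.8, power is only about 24% before any dilution.

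**Step 5. Cost of allocating room-mates together.** In the extreme case where all 18 are in enrolled pairs, the design effect is 1 + ICC. Effective sample size is 18/1.05 = 17.1, 18/1.10 = 16.4 or 18/1.20 = 15.0 for an assumed ICC of 0.05, 0.10 or 0.20. With only a few pairs the loss is smaller.

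**The case against.** The strongest reply is that the premise is conditional. The sentence on private space concerns confidential meetings with researchers. A reader might infer from it that participants do share rooms with one another and that the contrast will be diluted. The documents do not support that: they say only that someone may lack a private office, and that person's room-mate need not be enrolled. With at most 20 people from a whole building, there may be no enrolled pair at all. This stands, and it is why the point is worded as a possibility.

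Copying is also assumed. A room-mate's moving desk might equally remind someone to keep to their own schedule, and the step 10 reminders work against drift. This stands in part: prompts aimed at the right schedule reduce the risk, but they do not take away the competing cue.

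The joint educational sessions are stated outright and reach everyone, and six per group gives little power in any case. Both are true, and they keep the priority of this point low. Neither makes it harmless to leave room-sharing unrecorded.

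A reader might also infer that the planned analysis wrongly treats room-mates as independent. The protocol names no statistical model, so that cannot be said. It is only true that no handling of shared rooms is described.

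**Conclusion.** The gap is real but its consequence is conditional. The plan allows for participants without private offices, randomises individuals, keeps the desks in place for 6 months, and neither records nor limits room-sharing among those enrolled. Any two enrolled room-mates would more often than not be on different schedules (67% to 71%, depending on the allocation method).

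The resulting dilution runs from zero, if nobody shares, to about 6%, 12% or 18% for 1, 2 or 3 enrolled pairs with both members of each mismatched pair moving halfway. These figures rest on assumed pair counts and assumed copying, and should be read as a range of possibilities, not as a forecast. This is an inexpensive, optional improvement and not a flaw that undermines the trial.

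**What to change.** 1. At the eligibility contact, ask which room the volunteer works in and whether it is shared, and add this to the Excel list.
2. In item 4 of the recruitment outline, when more than 20 are eligible, draw at most one participant per shared room. Apply the rule across the male and female draws, since room-mates may be of different sex.
3. When item 5 applies and room-mates are both enrolled, preferably allocate them to the same schedule, account for room in the analysis and report the number of such pairs. This step is more debatable than the first two, because it places correlated people in the same group. It should not be adopted without the room term in the analysis.

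The cost is one extra column and one rule for the draw. A few volunteers may be passed over. In the fallback case there is a small loss of effective sample size and some constraint on balance with groups of 6. Steps 1 and 3 must be in place before the first allocation, and step 2 before the draw, because allocation cannot be repaired later. If nobody shares, the recorded rooms let the report rule this route out.

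### Does the risk section mean that only some groups track their standing?

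*Combined protocol and SAP*

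**What the plan says.** The protocol is an IRB questionnaire, and two parts of it speak to who records standing.

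The answer on possible risks and harms, under Expedited Review, lists inconveniences to participants and includes: "Depending on what group the participant is in, they will be asked to track how often they stand throughout the day". It adds that this might be inconvenient or uncomfortable.

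The Design section describes what is done:

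- The random-assignment step carries the note "all groups will attend same educational sessions".
- Step 7 reads "Provide educational sessions on use of sit-stand workstations and the behavioral monitoring self-report form".
- Step 9 collects the behavioral "monitoring self-report forms weekly from all participants".
- The standard-of-care answer says "All participants will be given the same questionnaires/surveys and behavioral tracking forms".
- The group-assignment answer says "The only difference in groups is in the instructions for alternating sitstand time".

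The answer justifying the expedited category adds a separate source of behavioural data: "The questionnaires will be assessing changes in behavior, movement at work, and discomfort at work".

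**The concern.** The risk sentence attaches the group condition to being asked to track, so on its face at least one group would not track. The Design section describes tracking that is common to all three groups. Taken literally, the two statements conflict.

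The stake would be the comparison itself. The trial sets out to compare sit-stand schedules, which requires the arms to be alike apart from the schedule. Recording one's own behaviour may change it; that is a general assumption, not something the document states. If one arm kept a weekly record and another did not, an effect of self-monitoring would be mixed with the effect of the schedule. With 6 people per group, no analysis could realistically separate them. A non-tracking arm would also lack the only frequent behaviour record that the document describes.

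**Working it through.** The plan gives no figure to reproduce on this point. The check is a comparison of texts, followed by the size of the worst case.

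**1. The statements side by side**

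| Place | Kind of text | Who tracks |
|---|---|---|
| Risks and harms answer | Description of inconvenience | Depends on group |
| Random-assignment step, with step 7 | Procedure | All groups are trained on the form |
| Step 9 | Procedure | Everyone, weekly |
| Standard-of-care answer | Procedure | Everyone, same forms |
| Group-assignment answer | Definition of the arms | Not listed as a difference |

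One descriptive sentence stands against four statements that define procedures or arms. Those four agree with each other.

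**2. Could staff act on the risk sentence?** It names no exempt group. With three groups, the number of ways in which some but not all of them track is 2³ − 2 = 6, and nothing in the document selects among these. Staff would have to invent the rule and also disregard step 9. The procedures can be carried out as written.

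**3. Is there a reading under which both hold?** The sentence answers a question about inconvenience. The group-assignment answer gives intervals of 20–30, 60 and 90 minutes. A participant who alternates at interval *t* starts one standing period every 2*t* minutes, which is 60/(2*t*) per hour:

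- *t* = 20 to 30: 60/40 = 1.5 to 60/60 = 1.0 per hour
- *t* = 60: 60/120 = 0.5 per hour
- *t* = 90: 60/180 = 0.33 per hour

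The procedures word the shortest schedule differently, as 20–30 minutes of standing in each hour, which gives 1.0 per hour. The two wordings must be reconciled as a separate matter. Under either one, the group with the most to record has at least 1.0/0.33 = 3 times as many standing periods as the group with the least. The burden of tracking therefore depends on group even when everybody tracks, and that is a plausible meaning of the sentence.

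**4. Size of the worst case.** Suppose one arm did not track. The document does not say when weekly collection ends, so I take 3 months (about 13 weeks) to 6 months (about 26 weeks) as the range. Forms lost in an arm of 6:

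- 6 × 13 = 78
- 6 × 26 = 156

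Each participant in that arm would still have 3 questionnaire rounds (baseline, 3 months, 6 months) and 1 workplace observation, so 3 + 1 = 4 assessments. If the procedures are followed, the number of forms lost is 0.

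**5. Role in the analysis.** The analysis answer says only that data will be coded and analysed with statistical software, and it gives the weekly forms no named role. Even the worst case cannot be tied to a stated outcome analysis.

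**The case for a change.** The strongest case for a change has three parts. First, the sentence says what it says: the condition governs the request to track, and if burden was meant, the wording is still wrong. Second, this is where the reviewing board reads about inconvenience, so it may understate a weekly task that every participant carries, however staff behave. Third, the remedy costs one sentence, while any ambiguity about equal treatment of arms touches the core of a three-schedule comparison.

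The first part stands as a remark on drafting. The second stands in part: the sentence is imprecise, but the same questionnaire tells the board that the forms go to all participants and come back weekly, so the task is disclosed. The consent pages are not available here, so nothing can be said about their wording. The third part does not carry the point. A cheap edit is worth requiring when it changes what is done or what can be concluded, and here the procedures already settle both.

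One further uncertainty counts against certainty on either side. The self-report form itself is not shown. That it records standing is inferred from its description and from the absence of any other tracking tool.

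**Conclusion.** The mismatch in wording is real, but it is a clerical slip and no change to the plan follows. The arms are defined and the tasks assigned in the Design section, which consistently treats tracking as common to all groups. The risk sentence neither assigns a task nor identifies an exempt arm, and it can be read as a loose remark that the burden varies with the interval.

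Under the procedures as written, the effect on data and comparison is nil. The 78 to 156 forms are the cost of a hypothetical arm that the document does not describe. This conclusion rests on two assumptions: that staff work from the numbered procedures, and that the tracking in the risk sentence is the weekly self-report form. A sponsor revising the document for other reasons could tidy the sentence, but the trial does not depend on it.

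### Where the sex quota applies, no use of sex is described at allocation or in analysis; with arms of 6 and 9+9 drawn, there is a 28% chance of an arm with at most one man or one woman

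*Combined protocol and SAP*

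**What the plan says.** All references are to the combined protocol questionnaire; there is no separate SAP.

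- Subjects, recruitment outline, item 4: "The team will draw 9-10 males and 9-10 females to participate".
- Same outline, item 5, which removes the quota when few are eligible: "In the event that there are 20 or fewer participants who are eligible all will be contacted to participate regardless of gender".
- Subjects, answer on equitable selection: "Attempts will be made to choose 50% males and 50% females for the study", followed by the expectation that "it is probable that we will have a higher percentage of females than males enrolled".
- Design, procedures list, the first of two steps numbered 5: "Randomly assign participants to one" of three groups. No sequence method, blocking or stratification is given.
- Subjects, sample size rationale: "This study will consist of 3 groups of 6 individuals receiving the sit-stand workstation", with the total limited by donated equipment: "And 18-20 workstations is the max that we can receive".
- Design, group assignment: "The only difference in groups is in the instructions for alternating sitstand time".
- Design, data analysis: a statistical software program will be used. No model, covariate or stratum is named.

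**The concern.** The plan handles sex with some care when choosing who takes part and then does not mention it again. Allocation is where the composition of each arm is settled, and arms of 6 are small enough for a simple random split to leave them visibly different.

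The sit-stand instruction is meant to be the only difference between arms. If sex is related to discomfort or movement at work, or to how these change, a difference in sex mix enters the comparison of schedules. With 4 men in one arm and 2 in another, the proportions differ by 2/6, so one third of any sex effect is carried into that comparison. With 4 against 1 it is 3/6, or one half. No adjustment is planned, and 18 to 20 people leave little room to sort this out afterwards.

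**Working it through.** **The plan's own figures.** 3 arms × 6 = 18. The quota gives 9 + 9 = 18 up to 10 + 10 = 20, which agrees with the stated equipment limit. There is no power calculation to reproduce.

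**Method.** Under simple random allocation to arms of fixed size 6, the probability that the arms receive a, b and c men out of M is C(6,a)·C(6,b)·C(6,c) / C(18,M).

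**Case 1: quota met, 9 men and 9 women.** The denominator is C(18,9) = 48,620.

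| Men per arm (any order) | Ways | Probability |
|---|---|---|
| 3, 3, 3 | 20³ = 8,000 | 16.5% |
| 4, 3, 2 | 6 × 15 × 20 × 15 = 27,000 | 55.5% |
| 4, 4, 1 | 3 × 15 × 15 × 6 = 4,050 | 8.3% |
| 5, 2, 2 | 3 × 6 × 15 × 15 = 4,050 | 8.3% |
| 5, 3, 1 | 6 × 6 × 20 × 6 = 4,320 | 8.9% |
| 5, 4, 0; 6, 2, 1; 6, 3, 0 | 540 + 540 + 120 = 1,200 | 2.5% |

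The ways add to 48,620.

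- Every arm has 2 to 4 of each sex: 35,000/48,620 = 72.0%.
- Some arm has at most one man or at most one woman: 13,620/48,620 = 28.0%.
- Some arm is of one sex only: 1,200/48,620 = 2.5%.
- Exact balance is lost in 40,620/48,620 = 83.5%, which is simply the complement of 16.5%. About two thirds of that (27,000/40,620 = 66.5%) is the mild 4, 3, 2 split.

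**Case 2: totals of 19 or 20.** Arm sizes are assumed. With 19 people as 7/6/6 (9 or 10 men), the chance of an arm with at most one of a sex is 26.3%. With 20 as 7/7/6 (10 men), it is 20.2%.

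**Case 3: fewer men.** The mix is illustrative, since the documents give none. With 6 men and 12 women, the denominator is C(18,6) = 18,564. By inclusion and exclusion, the ways to leave some arm without men are 3·C(12,6) − 3·C(6,6) = 2,772 − 3 = 2,769, so the probability is 14.9%. The same calculation gives 27.5% with 5 men (2,358/8,568) and 47.1% with 4 (1,440/3,060).

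**Effect of assigning within sex.** In blocks of three, 9 + 9 gives 3 and 3 in every arm, so 28.0% becomes 0. With 6 + 12, every arm gets 2 men and 4 women, so 14.9% becomes 0. With 5 or 4 men, one full block still puts a man in each arm.

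**Why leftovers need a rule.** With 7 men and 11 women, full blocks place 2 men and 3 women in each arm and leave 1 man and 2 women. If these are placed independently, the man joins the one arm without a leftover woman with probability 1/3 (giving 6/6/6); otherwise the arms are 7/6/5, probability 2/3. The same holds for 8 + 10. With 10 + 10, the two leftovers share an arm with probability 1/3, giving 8/6/6. Pooling the leftovers in one final block prevents both.

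**The case against.** The case against has force on several counts.

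- **Purpose of the quota.** A reader might infer that the quota was designed to balance the arms and that allocation then wastes it. The documents do not support this. The 50:50 target answers a question about equitable selection and is called an attempt. Randomising without sex strata contradicts no stated aim.
- **Balance at entry may never exist.** The quota lapses if 20 or fewer are eligible, and the plan itself expects more women. The 9 + 9 figures apply only where the quota does.
- **Probably lost is not badly lost.** The 83.5% could be taken to mean that serious imbalance is likely. It counts every departure from 3/3/3, and the commonest result is 4, 3, 2.
- **Bias.** A reader might call an uneven split confounding in the sense of bias. Chance imbalance under randomisation is not systematic bias.
- **Change scores.** The questionnaires are given at baseline, 3 and 6 months, and the Expedited Review section says they assess changes. A stable sex difference in level would then largely cancel, so sex would have to predict change. No link between sex and either level or change is stated.
- **Silence.** The documents do not say that sex is ignored; they describe no allocation method at all.

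All of this limits the point, but none of it removes it. Whoever prepares the allocation has no instruction on sex, the trial is run once with 6 per arm, and fewer men makes an arm without men more likely.

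**Conclusion.** The point stands as a minor, inexpensive improvement. Where the quota applies, the plan describes no use of sex after selection. With 9 + 9, exact balance in every arm has a 16.5% chance, and an arm with at most one man or one woman has a 28.0% chance (20.2% to 26.3% for totals of 19 or 20). Without the quota, the chance of an arm with no men is 14.9% at 6 men and 12 women, and it rises as men become fewer.

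These figures assume simple random allocation to arms of fixed size, the sex mixes stated, and assumed arm sizes above 18. That the imbalance would affect conclusions is a further assumption, because it requires sex to be related to the outcomes or their change. The plan's validity on average is not in question.

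**What to change.** In the allocation step of the procedures list:

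1. Randomise after consent. The list now places assignment before the consent meeting, so refusals could undo any balance.
2. Randomise men and women separately, in blocks of three with one person to each arm.
3. Pool the leftover men and women in one shared final block, so that arms stay at 6 each with 18 people, 7/6/6 with 19 and 7/7/6 with 20. If four are left over (for example 8 men and 11 women among 19), the arm that takes two should take one of each sex.
4. Use the same rule when the quota lapses and the sex split is unequal.

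In the data analysis answer, include sex as a stratum or covariate in the between-arm comparison.

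The cost is one degree of freedom in a sample of 18 to 20 and a little list preparation. The recruitment outline describes a single Excel list with contact details, so sex has to be added to it, but it must be known anyway to make the draw. No extra participants, visits or equipment are needed. The balance holds at assignment only; later withdrawals can still disturb it.
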